8.7. Pre-Hospital Discharge

Perform the following tests of the EV ICD System at the pre-hospital discharge. Prior to the subject being discharged, VF Therapies are required to be programmed ON and pacing therapies, as appropriate, should be programmed ON.

8.7.1. ECG Holter Monitoring

Set up DR220 Holter as described in section 8.6.5 prior to testing of the EV ICD System. Ensure the antenna is placed over the dressing of the device.

8.7.2. Electrical Testing

Perform Electrical Testing (Sensing, Impedance and Pacing Tests) as outlined in Section 8.8.3.

8.7.3. Provocative Testing

Perform the following elements of provocative testing as the subject is able:

- Electrical testing in different postures per Section 8.8.4.1
- Sinus rhythm in different postures per Section 8.8.4.2
- Maneuvers per Section 8.8.4.3

8.7.4. Imaging

Collect the radiographs at pre-hospital discharge per Table 6. Additional radiographs may be collected at the discretion of the physician in additional postures (i.e. prone, left decubitus, right decubitus) at any post-implant time point if electrical testing at follow-up reveals deterioration in sensing or pacing performance. Additional imaging at different postures is recommended if:

- Pacing output changes by 3V in magnitude in either direction (pacing testing performed in 1V increments); or
- R-wave amplitude falls by 50% or falls below 1mV.

Table 6: Image collection during Pre-Hospital Discharge Visit.

Visit	Image Collection
Pre-hospital Discharge Visit	
 • Supine AP → Tidal Inhalation and Tidal Exhalation • Supine LAT → Tidal Inhalation and Tidal Exhalation • Standing AP → Tidal Inhalation only • Standing LAT → Tidal Inhalation only

All images should be transferred in DICOM format.

[figure not shown]
If additional images (CT scans, radiographs, TEE, MRI or other imaging modalities) are collected at physician discretion throughout the duration of the study, it is requested that a copy of the images be sent to Medtronic.

8.7.5. Medications

Changes to oral or intravenous medications will be recorded.

8.8. Scheduled Follow-up Visits

Subjects will undergo assessments at scheduled follow-up visits to characterize the safety and efficacy of the EV ICD System. These assessments include:

- Electrical Testing per section 8.8.3 (electrical stability and acceptability of pacing threshold and pacing at safety margin)
- Provocative testing per section 8.8.4 (Ensure adequate sensing in ambulatory setting)
- Collection of imaging per section 8.8.5 – (mechanical stability)
- Holter monitoring per section 8.8.2 (on site) and 8.8.6 (24 Hour) – (electrical stability)

Medtronic will provide the target dates and window for each follow-up visit to the implanting center. Follow-up visit windows open on the Window Start date and remain open as defined in Table 7. It is recommended that subjects are scheduled as close as possible to the target date for a given follow-up visit.

Table 7: Scheduled visit windows.

Study Follow-up Visit	Window (Calculated days post-implant procedure)		
	Window Start (days post-procedure)	Target (days post-procedure)	Window End (days post-procedure)
2 Weeks	10	14	21
4-6 Weeks	28	30	49
3 Month	90	90	120
6 Month	180	180	210
12 Month (1 Year)	335	365	395
18 Month	518	548	578
24 Month (2 Year)	701	730	760
30 Month	883	913	943
36 Month (3 Year)	1066	1096	1126
42 Month	1248	1278	1308
48 Month (4 Year)	1431	1461	1491

All subjects with an implanted EV ICD System will remain in the study and be followed at pre-defined study visits until official study closure. After their study participation ends, the EV ICD System will remain implanted and the subject will be provided with standard medical care by their physician.

8.8.1. Wound Inspection (2 Weeks, 4-6 Weeks, 3 Months)

Visually inspect the device Pocket Incision and the Lead Incision for appropriate recovery. Obtain photographs of the pocket area and the Lead Incision area per section 8.8.5.2.

8.8.2. On Site ECG Holter Monitoring (2 Weeks, 4-6 Weeks, 3 Months)

A DR220 Holter monitor will be used to continuously monitor device ECG during all in-office follow-up visits up through the 3-Month visit.

2 Weeks, 4-6 Weeks, 3 Month Visits: Set up Holter according to Figure 8.3 prior to testing of the EV ICD System.

[figure not shown]

Figure 8.3: Example of DR 220 Holter system set-up for continuously collecting device ECG data and body-surface ECG data during in-office follow-ups (2 Weeks, 4-6 Weeks, and 3 Month visits) and 24-hour Holter (at 4-6 Weeks and 3 Month follow-ups).

8.8.3. Electrical Testing (2 Weeks, 4-6 Weeks, 3 Months)

Subjects' medical records should be made available prior to performing electrical testing. Interrogate the device by selecting "Interrogate ALL" on the 2090 programmer at the beginning of the visit. Save the data via a Save-to-media file.

Perform the following tests while the subject is in the postures described in section 8.8.4.1.

8.8.3.1. Sensing Testing

Adjust sensing parameters to avoid T-wave oversensing, P-wave oversensing or other oversensing. Once configured, execute the Sensing Test while running the 2090 strip chart recorder. Print the Sensing Test Report on the 2090 Programmer, and send a copy of live strips and report to Medtronic.

If R-wave has deteriorated ($<1\text{mV}$), evaluate alternate sensing vectors and program sensing settings as desired. Ensure R-wave in selected sensing vector is $\geq 1\text{mV}$ in all postures. If R-wave $\geq 1\text{mV}$ cannot be maintained in any of the vectors, consider assessment of lead movement via imaging and system modification if necessary.

8.8.3.2. Impedance Testing

Subthreshold impedance will be measured for the following electrode pairs:

- Ring1-Ring2
- Ring1-Coil2
- High Voltage

Print the Lead Impedance Test Report on the 2090 Programmer and submit a copy to Medtronic.

8.8.3.3. Pacing Testing

Using a Pulse Width Search, conduct pacing capture threshold (PCT) test until lowest voltage pacing threshold is found. Continue pacing testing up to 30V to determine extracardiac muscle stimulation threshold. The following configurations may be evaluated: Ring 1-Coil2, Ring1-Ring2, Coil2-Coil1.

At the conclusion of pacing capture threshold testing, the subject's device should be programmed after confirming extracardiac stimulation threshold while awake to allow for an assessment of the margin between pacing capture threshold and extracardiac stimulation. If post pace oversensing is observed, sensing parameters should be adjusted to eliminate or minimize oversensing.

Print final capture threshold report and final parameters and send a copy to Medtronic.

8.8.4. Provocative Testing (2 Weeks, 4-6 Weeks, 3 Months)

All subjects are encouraged to perform all postures and maneuvers. If the subject is physically unable to complete or perform a posture or maneuver, this should be documented, however, a study deviation will not be required.

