Study procedure	B/L	IMP	PHD	2 WKS	4-6 WKS	3 MO	6, 12, 18, 24... MO	U'SCH	SYS MOD	EXT
Informed Consent	X									
Inclusion/Exclusion Assessment	X									
Physical Exam, Demographics, Cardiovascular Medical History	X									
Surface ECG	X*	X [†]							X [^]	
Surgical history	X									
System and procedure information		X							X	
Fluoroscopy recordings during tunneling procedure		X							X [^]	
Fluoroscopy (AP and Lateral) of final ICD generator and lead position (cine preferred)		X							X [^]	
On site ECG monitoring (DR220 Holter)		X	X	X	X	X			X [^]	
Sensing, Impedance & Pacing Tests		X					X		X [^]	
Defibrillation Testing		X							X [^]	
Provocative testing (postures): (Sensing, Impedance and Pacing tests)			X	X	X	X				
Provocative Testing (Maneuvers)			X	X	X	X				
Provocative Testing – brisk walk				X	X					
Provocative Testing – Regular Treadmill						X				
Cardiac-gated CT	X					X (w/o contrast)				
Radiographs – Standing and Supine, AP & LAT, tidal Inhalation and Exhalation			X		X	X				
Echocardiogram	X*		X							

x if required by local law, women of child-bearing potential must undergo a pregnancy test within seven days prior to EV ICD Pilot Study procedures

EV ICD Pilot Study Clinical Investigation Plan

MDT17034

Version 1.0, 02-MAR-2018 Page 16 of 133

24-hour Holter Monitoring (DR220 Holter)					X	X				
Pocket/ incision photographs			X	X	X	X	X [#]	X [#]	X	
Save-to-media files		X	X	X	X	X	X	X	X	
Medications	X	X	X	X	X	X	X	X	X	X
Adverse Events (including AEs with fatal outcome), Device Deficiencies, Study Deviations, Other Imaging, and Subject Exits		As they occur								

* Within 30 days prior to consent is acceptable [†] If available, collected through EP recording system during procedure [#] Recommended if infection related to the EV ICD System is suspected [^] System modification where a subject leaves with an EV ICD System
										
Safety Assessments	All Adverse Events that are procedure related, system related, accessory related, Holter related, cardiovascular related, or serious that occur from the time of enrollment through study exit will be collected and reported to Medtronic during the study. Additionally, any device deficiency related to the EV ICD System will be collected.									
Statistics	Descriptive statistics will be used to summarize all endpoints. For some endpoints such as lead position and pacing testing, multiple measurements per subject will be assessed and compared.									

3. Introduction

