8.8.4.1. Electrical Testing in Different Postures

Conduct electrical tests described in section 8.8.3 whilst the subject is in each of the following postures:

- Sitting in the upright position (standing is also allowed)

- Bent over from sitting in chair with both hands touching or reaching for the ground
- Supine
- Prone (or simulated prone during PHD visit)
- Lying on left side (if possible)
- Lying on right side

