12.6.4. Analysis Methods

Results will be summarized in aggregate using descriptive statistics. Pacing testing will be done at the postures provided in section 8.8.4.1. For each posture, and each follow-up visit, the proportion of subjects undergoing pacing testing will be reported, as well as the proportion for whom capture is obtained.

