### 7.9.4.4 Analysis Methods

Results will be summarized in aggregate using descriptive statistics. Pacing testing will be done at the postures provided in section 8.8.4.1. For each posture, and each follow-up visit, the proportion of subjects undergoing pacing testing will be reported, as well as the proportion for whom capture is obtained.

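### Posture results are planned only as separate capture proportions, so a difference between postures can reflect who was tested; state the denominator and add a within-subject comparison (minor).

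*Protocol*

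**What the plan says.** **Testing.** Protocol 8.8.4.1 lists six postures for the sensing, impedance and pacing tests: sitting, bent over, supine, prone, left side and right side. Section 8.8.4 says "All subjects are encouraged to perform all postures and maneuvers", but also "If the subject is physically unable to complete or perform a posture or maneuver, this should be documented", and adds that such an omission is not a deviation. At pre-hospital discharge (8.7.3) the instruction is "Perform the following elements of provocative testing as the subject is able". The left-side posture is marked as conditional in the list itself.

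**Analysis set.** Protocol 12.6.5 and SAP 7.9.4.5 include any successfully implanted subject with pacing tests in at least one posture.

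**Method.** SAP 7.9.4.4, identical to protocol 12.6.4, gives descriptive statistics in aggregate and then one specific summary by posture and visit: "the proportion of subjects undergoing pacing testing will be reported, as well as the proportion for whom capture is obtained". The denominator of the second proportion is not given.

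**Stated intention.** The Statistics row of the protocol synopsis (Section 2) says: "For some endpoints such as lead position and pacing testing, multiple measurements per subject will be assessed and compared". Neither 12.6.4 nor SAP 7.9.4.4 says how.

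**Missing data.** SAP 7.4 rules out imputation for primary and secondary efficacy analyses and does not mention ancillary objectives. SAP 7.2 deals with subjects who do not complete a visit, not with a posture missed within a visit.

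**The concern.** Each subject is meant to be tested in several postures at the same visit, so each can serve as their own control. Once some omit a posture for physical reasons, the proportions for two postures at one visit come from different sets of people. If those who cannot take a posture also differ in how readily they capture, the two proportions will differ even where posture has no effect.

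The stated rationale of the objective is performance over time and at different postures, and protocol 5.2 expects the pilot to guide programming in the pivotal study. A reader will naturally compare the posture columns. With 20 to 35 implanted subjects, one subject is 1/20 = 5 points or 1/35 = 2.9 points, so a few omissions can move a column visibly.

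**Working it through.** The documents give no capture rate, posture-completion rate or computed figure for this objective, so there is nothing to reproduce. The check asks what the planned summary would show if posture had no effect at all.

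**Inputs.** N = 20 to 35 implanted (protocol 12.2, SAP 6). Assumed: m subjects unable to take one posture; capture probability a in subjects able to take it and u in those unable; everyone can take the reference posture.

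**Formulas, no true posture effect.**
- Reference posture, all tested: [(N - m)a + m·u] / N
- Restricted posture, tested subjects as denominator: a. Apparent difference = (m/N)(a - u)
- Restricted posture, all subjects as denominator: (N - m)a / N. Apparent difference = -(m/N)u
- Paired, subjects tested in both postures: a - a = 0

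**Worked case, N = 20, m = 4, a = 95%, u = 50%.**
- Reference: (16 × 0.95 + 4 × 0.50)/20 = 17.2/20 = 86.0%
- Restricted, tested denominator: 95.0%, a difference of +9.0 points
- Restricted, all-subjects denominator: 15.2/20 = 76.0%, a difference of -10.0 points
- Paired: expected difference 0

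N = 35 with m = 7 gives the same differences, because only the share m/N enters.

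**Range (a, u and m/N all assumed; differences in percentage points).**

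| Share skipping | Capture, able v unable | Tested denominator | All-subjects denominator | Paired |
|---|---|---|---|---|
| 10% | 95% v 85% | +1.0 | -8.5 | 0 |
| 10% | 95% v 70% | +2.5 | -7.0 | 0 |
| 20% | 95% v 95% | 0 | -19.0 | 0 |
| 20% | 95% v 70% | +5.0 | -14.0 | 0 |
| 20% | 95% v 50% | +9.0 | -10.0 | 0 |
| 30% | 95% v 50% | +13.5 | -15.0 | 0 |

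The two denominators give artefacts of opposite sign in every row where skippers capture less often than performers. With all subjects in the denominator, a difference appears even when ability is unrelated to capture, because an untested subject counts as one without capture.

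**The case against.** Much of the other side stands.

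- **The plan shows how many were tested.** The proportion tested is reported for every posture and visit, omissions must be documented, and SAP 7.4 puts all available data in listings and tabulations. A reader will see where the sets differ, and could convert an all-subjects figure if its denominator were known (76.0% / 80% = 95%). What stays hidden in the summary is who is missing and how they performed in a posture they could take.
- **The mechanism is limited.** Only physical inability excuses an omission. The exclusion criteria (protocol 7.4) cover BMI above 40 within severe obesity, decompensated heart failure and oxygen-dependent COPD. Prone may be simulated at discharge, and standing may replace sitting. Skipping may be rare.
- **Large gaps in capture are doubtful.** Protocol 3.1 reports that an acute study in 26 subjects found substernal pacing should be possible in nearly all patients. One can build an 80% v 100% contrast at N = 20 by letting all four skippers fail to capture supine, but that is an extreme case and not a fair guide to size.
- **Nothing is tested.** There is no hypothesis and no planned estimate of a posture difference, so a gain in precision from pairing is not a reason for change here. The general phrase about descriptive statistics neither excludes pairing nor commits to an unpaired analysis.
- **Pairing has its own limit.** It describes only those who could take the posture. How the posture performs in the others stays unknown.

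A reader might infer that the plan makes difficult postures look better than they are. The documents do not support that: the direction depends on a denominator they do not state. A reader might also infer that within-subject comparison was overlooked. It was not; the synopsis announces it, and the methods sections do not carry it through.

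**Conclusion.** The concern holds as a minor point. Omission is permitted, the sets can differ by posture, and the only specified posture summary cannot separate the effect of posture from the effect of who was tested.

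With tested subjects as denominator, the artefact runs from 0 when ability is unrelated to capture, through about 1 point in a mild case, to 9 points for 20% skipping at 95% v 50%. With all subjects as denominator it reverses, to -10 points in that last case. Every rate here is assumed; the true size and sign cannot be known from the documents. Restricting to subjects tested in both postures removes the composition artefact in all these scenarios.

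The consequence is confined to an ancillary, descriptive objective. Neither the 90-day freedom from major complications nor the defibrillation testing success rate is touched.

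**What to change.** In SAP 7.9.4.4 and protocol 12.6.4:

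1. State that the capture proportion is taken among subjects tested in that posture at that visit.
2. Name a common reference posture, for example supine. For each visit and each other posture, among subjects tested in both, report the paired capture table (both, reference only, posture only, neither) and the within-subject differences in pacing threshold, impedance and R-wave amplitude.
3. Beside it, show the reference-posture results of subjects who omitted that posture, so that a reader can judge whether they differ from those tested.
4. Keep the planned proportions tested and captured as they are.

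This carries out the synopsis's per-subject comparison with data already collected and needs no extra testing. The cost is a short change of wording, one more table, and paired sets slightly smaller than the marginal ones. The choice of supine is a convenience; any posture that nearly all subjects can take would serve, provided it is fixed in advance.

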8.8.4.1. Electrical Testing in Different Postures

Conduct electrical tests described in section 8.8.3 whilst the subject is in each of the following postures:

- Sitting in the upright position (standing is also allowed)

- Bent over from sitting in chair with both hands touching or reaching for the ground
- Supine
- Prone (or simulated prone during PHD visit)
- Lying on left side (if possible)
- Lying on right side

8.8.4.2. Sinus Rhythm in Different Postures

Collect sinus rhythm data (for approximately one minute) whilst the subject is in each of the following postures:

- Sitting in the upright position (standing is also allowed)
- Bent over from sitting in chair with both hands touching or reaching for the ground
- Supine
- Prone (or simulated prone during PHD visit)
- Lying on left side (if possible)
- Lying on right side

8.8.4.3. Maneuvers

Request the subject to perform each of the following maneuvers to determine the effect(s) on sensing (if any):

- Heavy coughing (approximately 10 times), while sitting or standing
- Valsalva maneuver (2 times)

For approximately 1 minute:

- Sawing action (left-hand, roughly 3 times per second) while sitting or standing
- Deep breathing while sitting or standing
- Simulate brisk walking, e.g., marching in place
- Pressing hands together and harder to create muscle noise
- Star jumps (i.e., jumping jacks)
- 4-6 Weeks and 3 Month visits only: manipulate device (e.g., gently wiggling the device repeatedly) to look for changes in sensing due to mechanical movement

Subjects will be allowed to have recovery time after each maneuver as needed.

8.8.4.4. Brisk Walk and Treadmill (2 Weeks, 4-6 Weeks and 3 Months)

Subjects will perform a brisk walk or treadmill test, and are allowed recovery time after as needed.

2 Week and 4-6 Weeks: Brisk walk - Have the subject walk as briskly for 3-5 minutes as the patient finds tolerable to increase heart rate for approximately three minutes in an open hallway

3-Months: Treadmill – Have the subject run at speed on a treadmill for 3 to 6 minutes, as tolerated

Interrogate the device by selecting “Interrogate ALL” on the 2090 programmer at the end of the visit. Save the data via a Save-to-media file.

8.8.5. Imaging (4-6 Weeks, 3 Months)

8.8.5.1. Radiographs and CT Scans

Cardiac-gated CT scan (respiratory cycle for CT: tidal inhalation only) is to be performed during the 3 Month follow-up visit. Contrast is not required. It is recommended that prospective gating (best diastole phase of the cardiac cycle) be used to reduce radiation dose to the subject.

- The CT image should include the thorax from the collarbone to the inferior aspect of the ribcage and include the entire width of the torso, i.e., side-to-side, and the implanted ICD device.
- The slice thickness should be ≤ 1.2 mm (≤ 0.8 mm preferred).
- The in-plane resolution should be ≤ 0.7 mm (≤ 0.5 mm preferred).

All radiographs will be collected in the anterior-posterior (AP) and lateral (LAT) configurations as specified in Table 8.

Additional radiographs may be collected at the discretion of the physician in additional postures (i.e. prone, left decubitus, right decubitus) at any post-implant time point if electrical testing at follow-up reveals deterioration in sensing or pacing performance. Additional imaging at different postures is recommended if:

- Pacing output changes by 3V in magnitude in either direction (pacing testing performed in 1V increments); or
- R-wave amplitude falls below 1mV, or falls by 50% of previous measurement.

Table 8: Image collection during follow-up period.

Visit	Image Collection
4-6 Weeks	
 • Supine AP → Tidal Inhalation and Tidal Exhalation • Supine LAT → Tidal Inhalation and Tidal Exhalation • Standing AP → Tidal Inhalation only • Standing LAT → Tidal Inhalation only
3 Months	Cardiac-gated CT (no contrast) (Respiratory cycle for CT: tidal inhalation only)
	
 • Supine AP → Tidal Inhalation and Tidal Exhalation • Supine LAT → Tidal Inhalation and Tidal Exhalation • Standing AP → Tidal Inhalation only • Standing LAT → Tidal Inhalation only

All images should be transferred in DICOM format.

If additional images (CT scans, radiographs, TEE, MRI or other imaging modalities) are collected at physician discretion throughout the duration of the study, it is requested that a copy of the images be sent to Medtronic.

8.8.5.2. Photographs (2 Weeks, 4-6 Weeks, 3 Months)

If allowed per local regulations and accepted by the subject in the Informed Consent, photographs of the sternal incision site and the device pocket using a supplied camera will be requested for training, education, and/or research purposes. These photographs will not display any identifiable features of the subject.

Additionally, photographs of the device pocket and sternal incision are recommended at any subsequent scheduled visits in which infection related to the EV ICD System is suspected or previously diagnosed. Report any adverse events per Section 10.

8.8.6.24 Hour Holter Monitoring (4-6 Weeks, 3 Months)

The DR220 Holter monitor will be set up according to Figure 8.3 for 24-hour Holter monitoring at the 4-6 Week and 3 Month Visits.

During the 24-hour Holter Monitoring assessment, the subject may leave the study site (e.g. return home) and should go about their activities of daily living (ADL). Each subject will receive a subject activity log and be instructed to document the time of day and a variety of pre-populated ADLs including, but not limited to, 'exercise' or 'sleep'. The subject will be instructed to return the activity log, Holter monitor leads, recorder and memory card at the end of the 24-hour assessment period. The Holter data should be transmitted to Medtronic.

